### 8.3 Study Timeline

Time point	Study period						Visit 4 24 weeks ± 3 days
	Screening	Intervention					
Time	Screening visit	Visit 1	Visit 2, * (Touch-up)	Visit 2, 2 weeks ± 3 days	Visit 3 4 weeks ± 3 days		
Informed consent	×						
Eligibility Criteria	×						
Randomization and allocation		×					
Medical History	×						
Face photography	×	×		×	×	×	×
Intervention		×		×			
NLF severity score assessment	×			×	×	×	×
PGAIS assessment		***		×	×	×	×
Concomitant Medications	×	×		×	×	×	×
Adverse Events reporting	×	×		×	×	×	×

\* Two treatments will be allowed over a 2-week period (initial treatment plus one touch-up) to achieve optimal correction of the NLFs. The level of correction will be assessed by the evaluating investigator at week 2 after the initial treatment and, if less than optimal, the treating investigator will be directed to retreat the under corrected NLF(s).

\*\* This visit is only conducted in patients with touch-up injection.

\*\*\* PGAIS in visit 1 is assessed after the intervention.

## **8.4 Variables**

The primary objective of this study is effectiveness assessment, including the mean level of improvement from baseline in NLF severity score by WSRS at week 24. The secondary outcomes of this study are to evaluate other effectiveness and safety parameters, including the number of subjects with improvement score in PGAIS at week 24 compared to baseline, the proportion of NLFs maintaining a clinically significant improvement in NLF severity score ( $\geq 1$ -point reduction from baseline) at week 24, the volume required for optimal cosmetic result (initial treatment + touch-up), the number of NLFs receiving touch-up treatment, and the incidence of adverse events (injection site reactions) based on their severity.

Variables in this study include patient demographic information (age, sex), history of filler injection, WSRS at each visit, patient's medical history, patient's medications, injection volume, receiving touch up treatment, PGAIS at each visit.

The intensity of AEs will be graded according to the CTCAE v5.0, and terminology for AEs will be chosen according to the MedDRA system organ class and preferred term (MedDRA Desktop Browser 4.0 Beta). Seriousness will be also recorded for all AEs.

## **8.5 Data Sources and Measurement**

All data will be collected by specialists and recorded in a booklet comprising five visits. The baseline information (demographics, past medical history, history of filler injection, patients' medications), intervention information (e.g., dosage at visit1 and touch up), WSRS, and PGAIS will be recorded. All AEs will be reported based on the Medical Dictionary for Regulatory Activities (MedDRA) terms as the preferred term (PT) and system organ class (SOC) (14). All reported AEs will be graded according to the common terminology criteria for adverse events v5.0 (CTCAE v5.0) (15). Moreover, the seriousness of AEs will be specified using ICH-E2B guidelines (16). The causality relation will be assessed based on the World Health Organization (WHO) criteria (17).

## **8.6 Study Size**

In an equivalence test of means using two one-sided tests on data from a paired design, a sample size of 97 achieved 80% power at a 2.5% significance level. When the true difference between the means was 0.000, the standard deviation of the paired differences was 0.510, and the equivalence limits were -0.170 and 0.170. Considering a drop-out rate of 10%, total sample size required is 108.

## **8.7 Statistical Methods**

### ***8.7.1 Main Summary Measures***

The descriptive analysis will be performed using frequency and percentage for categorical variables and mean and standard deviation for continuous variables.

### ***8.7.2 Main Statistical Methods***

The mean level of improvement from baseline in NLFs severity score based on assessments by evaluating investigators and the injection volume to obtain optimal result will be analyzed using either a paired t-test or a signed-rank test.

The number of patients with an improved score for the PGAIS, proportion of NLFs with clinically significant improvement and the number of NLFs receiving touch-up treatment will be analyzed using a McNemar test.

The safety data will be analyzed primarily using summary statistics. Summary statistics are included the number of subjects (number and percentages) and then classified according to system organ class and preferred term for AEs and SAEs. The incidence of the preferred term for grades 3 and 4 of AEs will be reported. Moreover, causality will be assessed and its results will be reported by frequency and percentage.

## **8.8 Quality Control**

Espad Pharmed Co. conducts this study according to procedures that incorporate the ethical principles of GCP. The investigators participating in this study are among the most professional dermatologists in Iran.

Before initiating the study, the PMS booklet will be checked and confirmed by the principal investigator regarding conformity with the study protocol. An instruction manual will be provided to train the personnel involved in filling the booklets. Participants' recorded data in PMS booklets will be regularly monitored in terms of verification and validity. The recorded data in the booklets will be regularly exported and checked by a certified statistician for outlier determination to verify if data entry errors have occurred, and they will be rechecked if needed.

## **8.9 Limitations of the Research Methods**

The decision for a touch-up injection can be participant-driven rather than based on a real need to achieve optimal aesthetic results.

## **9 Protection of Human Subjects**

This study will be conducted in full conformance with the principles of the Declaration of Helsinki and GCP, along with local ethical approval requirements. Ethical approval is obtained from the local ethics committee of the affiliated university of the principal investigator. An informed consent form will be signed by the candidates who voluntarily accept to participate in the study. All personal data will be confidentially recorded and archived during the study and thereafter.

## **10 Management and Reporting of Adverse Events/Adverse Reactions**

### **Adverse Event (AE)**

Any untoward medical occurrence in a patient or clinical investigation subject administered a pharmaceutical product and which does not necessarily have to have a causal relationship with this treatment.

### **Adverse Drug Reaction (ADR)**

All noxious and unintended responses to a medicinal product related to any dose should be considered adverse drug reactions.

All AEs will be classified based on their severity and in accordance with the approved guidelines in the CTCAE v.5, published on November 27, 2017. According to these guidelines, Grade refers to the severity of the AE. Accordingly, Grades 1 to 5 with unique clinical descriptions of the severity of each AE are specified as follows:

Grade 1 Mild; asymptomatic or mild symptoms; clinical or diagnostic observations only; intervention not indicated.

Grade 2 Moderate; minimal, local or noninvasive intervention indicated; limiting age-appropriate instrumental Activities of Daily Living (ADL).

Grade 3 Severe or medically significant but not immediately life-threatening; hospitalization or prolongation of hospitalization indicated; disabling; limiting self-care ADL.

Grade 4 Life-threatening consequences; urgent intervention indicated.

Grade 5 Death related to AE.

The causality relation will be assessed based on the WHO criteria. To determine the relationship between an AE or ADR and the treatment used in the study, the following definitions are considered:

#### **Unrelated**

An adverse event for which no relationship can be inferred between it and the drug under consideration.

#### **Related**

**Certain:** Event or laboratory test abnormality, with plausible time relationship to drug intake • Cannot be explained by disease or other drugs • Response to withdrawal plausible (pharmacologically, pathologically) • Event definitive pharmacologically or phenomenologically (i.e., an objective and specific medical disorder or a recognised pharmacological phenomenon) • Rechallenge satisfactory, if necessary

**Probable / Likely:** Event or laboratory test abnormality, with reasonable time relationship to drug intake • Unlikely to be attributed to disease or other drugs • Response to withdrawal clinically reasonable • Rechallenge not required

**Possible:** Event or laboratory test abnormality, with reasonable time relationship to drug intake • Could also be explained by disease or other drugs • Information on drug withdrawal may be lacking or unclear

**Unlikely:** Event or laboratory test abnormality, with a time to drug intake that makes a relationship improbable (but not impossible) • Disease or other drugs provide plausible explanations

**Conditional / Unclassified:** Event or laboratory test abnormality • More data for proper assessment needed, or • Additional data under examination

---

 Instrumental ADL refer to preparing meals, shopping for groceries or clothes, using the telephone, managing money, etc.

 Self-care ADL refer to bathing, dressing and undressing, feeding self, using the toilet, taking medications, and not bedridden.

**Unassessable / Unclassifiable:** Report suggesting an adverse reaction • Cannot be judged because information is insufficient or contradictory • Data cannot be supplemented or verified

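### Protocol Section 10 lists Unlikely and two undetermined causality categories under Related, so a related-event total taken from those headings can be inflated

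*Protocol*

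**What the plan says.** Protocol Section 10, under Adverse Drug Reaction, names the standard: "The causality relation will be assessed based on the WHO criteria". It then introduces the definitions that decide how an event relates to treatment. Two parallel headings follow.

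- **Unrelated** holds a single definition: "An adverse event for which no relationship can be inferred between it and the drug under consideration".
- **Related** holds six categories: Certain, Probable/Likely, Possible, Unlikely, Conditional/Unclassified and Unassessable/Unclassifiable.

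Unlikely is described as "Event or laboratory test abnormality, with a time to drug intake that makes a relationship improbable (but not impossible", followed by "Disease or other drugs provide plausible explanations". Conditional/Unclassified includes "More data for proper assessment needed, or" data still under examination. Unassessable/Unclassifiable includes "Cannot be judged because information is insufficient or contradictory".

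On output, Protocol Section 8.7.2 says that "causality will be assessed and its results will be reported by frequency and percentage". The SAP cites the WHO guidelines for causality (Section 3, Data sources and measurement) and says that the causality assessment will be reported (Section 7, Safety Analysis). It does not repeat the Related/Unrelated split. The causal relationship of adverse events is a listed secondary objective in both documents (Protocol Section 6; SAP Section 2).

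**The concern.** A category defined by an improbable relationship and a plausible alternative cause should not sit under a heading that says the event is related. The heading and the definition cannot both be applied. The two undetermined categories raise a softer version of the problem: nobody has judged those events to be related, yet the heading groups them with events that have been so judged.

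What is at stake is the meaning of any statement about related adverse events in the study report. Causality is a stated objective, and neither document says which categories count as related. An analyst asked for that number would find one two-way split on paper, in Section 10, and could apply it as printed. If the choice is left until after unblinding, it could also be made with the results in view.

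**Working it through.** No figure in the plan can be reproduced here, because the documents give no adverse event counts. The check is a comparison of the text followed by a counting identity.

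**Step 1. Each category against its heading (Protocol Section 10).**

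| Category under Related | What its definition says | Fits Related? |
|---|---|---|
| Certain, Probable/Likely, Possible | Plausible or reasonable timing | Yes |
| Unlikely | Improbable timing, plausible other cause | No, contradicts it |
| Conditional/Unclassified | Judgement pending | Undetermined |
| Unassessable/Unclassifiable | Judgement not possible | Undetermined |

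The boundary with Unrelated is also unclear. An event that cannot be judged arguably meets the Unrelated wording too, since no relationship can be inferred for it. Its side of the split could then depend on which label the assessor picks.

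**Step 2. Where causality is used.** Protocol Section 8.7.2 and SAP Section 7 both promise to report causality. Neither names a pooled count of related events or says whether the table has two rows or one per category. The SAP's chi-square comparison is of adverse events, not of related events.

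**Step 3. Counting identity.**

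- Related as printed = Certain + Probable + Possible + Unlikely + Conditional + Unassessable
- Related, narrow = Certain + Probable + Possible
- Excess = Unlikely + Conditional + Unassessable, which is zero or more

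If the three categories hold a share s of all N events, the related percentage rises by (s × N)/N = s.

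**Step 4. Size, under assumption.** Suppose, for illustration only, 40 events in total, of which 10 are Certain, Probable or Possible.

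| Assumed s | Events in the three categories | Related, narrow | Related as printed | Rise |
|---|---|---|---|---|
| 0% | 0 | 10/40 = 25% | 10/40 = 25% | 0 points |
| 10% | 4 | 10/40 = 25% | 14/40 = 35% | 10 points |
| 30% | 12 | 10/40 = 25% | 22/40 = 55% | 30 points |

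The total as printed can equal the narrow total or exceed it, but never falls below it.

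**Step 5. Comparison of products.** If the excess is a events for one product and b for the other, the difference in related counts shifts by a − b. With a = b it does not move, although the ratio of the two counts moves toward 1.

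**The case against.** The strongest reply is that no planned output depends on the heading. The WHO categories are the assessment scale, and reporting by frequency and percentage is most naturally read as one row per category. On that reading the heading changes no number, and the secondary objective is met without any pooling. This stands, and it is why the point is minor.

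A second reply is that Related may be meant as relationship not excluded. Unrelated is reserved for events where no relationship can be inferred, while Unlikely is worded as improbable but still possible. Counting undetermined events on the cautious side is a recognisable safety convention. For Conditional/Unclassified and Unassessable/Unclassifiable this has force: the documents do not show that grouping to be an error, only an unstated choice. For Unlikely it is weaker. The heading says related, the definition says improbable with another plausible explanation, and nothing in Section 10 says that Related means merely not excluded.

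A reader might infer something stronger: that every related-event count from this trial will be too high, and that the difference between the products will be diluted. The documents do not support either. There is no excess if no event falls in the three categories or if only individual categories are tabulated. Equal additions on both sides leave the absolute difference unchanged. Nor is the two-way split the only grouping on offer, because the six categories are themselves defined. Finally, neither document presents the related-event rate as the main safety result; Protocol Section 8.4 and the SAP synopsis put forward the incidence of injection site reactions by severity.

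**Conclusion.** Wrong as written, of minor severity. The clear error is Unlikely, which sits under a heading that its own definition contradicts. Mixing the two undetermined categories into Related is an unstated convention that should be made explicit.

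The size is conditional. A total taken from the Section 10 headings exceeds Certain + Probable/Likely + Possible by the number of events in the three categories, which may be zero. The shares of 10% and 30% used above are assumptions, and the documents offer nothing to narrow them. The conclusion also rests on someone producing a pooled total, which no section explicitly plans. Only descriptive safety reporting is affected; the primary equivalence analysis, its margin and the sample size are not.

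**What to change.** In Protocol Section 10:

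- Move Unlikely out of Related.
- Put Conditional/Unclassified and Unassessable/Unclassifiable under a separate heading for events whose causality is undetermined.

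In the SAP, Section 7, Safety Analysis, before unblinding:

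- Report every WHO category, and Unrelated, by product.
- State that any total labelled related is Certain + Probable/Likely + Possible.
- Show undetermined events on their own line. A conservative total that includes them can be added if the sponsor wants it, provided that it is labelled as such.

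The cost is a rewording of one protocol section and a short addition to the SAP. No new data are needed, because events are already to be assessed against the WHO criteria.

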## **Recording Adverse Events**

All AEs that occur following drug administration will be meticulously documented in the patient's medical records.

## **Seriousness of AEs will be assessed based on ICH-E2B guidelines**

### **seriousness criteria:**

- Results in death
- Is life-threatening
- Requires inpatient hospitalization or prolongation of existing hospitalization
- Results in persistent or significant disability/incapacity (as per reporter's opinion)
- Is a congenital anomaly/birth defect
- Other medically important condition

## **11 Plans for Disseminating and Communicating Study Results**

Study report will be prepared and submitted according to the ICH guidelines, and a journal article will be written to submit in peer-reviewed journals.

## 13 Appendices

Not applicable.

Methods used for assumptions to be checked for statistical methods	22
References	22

Synopsis

Title	A phase IV, randomized, double-masked, active controlled, within-Subject equivalency clinical trial to compare effectiveness and safety of Lunaphil Ultra (Hyaluronic acid, produced by Espad Pharmed Co.) versus Juvéderm® Ultra 4 (Hyaluronic acid, produced by Allergan Co.) for the management of moderate or severe nasolabial folds (NLFs)
Aim of Study (Primary endpoint)	The Primary objective of this study is to verify the effectiveness of Lunaphil Ultra (produced by Espad Pharmed Co.) compared with Juvéderm® Ultra 4 by mean level of improvement from baseline in NLF severity score
Secondary objectives	The secondary objectives of this study are to verify the effectiveness and safety of Lunaphil Ultra (produced by Espad Pharmed Co.) compared with Juvéderm® Ultra 4
Study Design	The study is designed as phase IV, randomized, double-masked, active controlled, within-Subject equivalency clinical trial with primary endpoint of mean level of improvement from baseline in NLF severity score
Sponsor	Espad Pharmed Company
Investigational Drug	Lunaphil Ultra (produced by Espad Pharmed Co.)
Comparator	Juvéderm® Ultra 4 (the reference drug, produced by Allergan Co.)
Sample size	In an equivalence test of means using two one-sided tests on data from a paired design, a sample size of 97 achieves 80% power at a 2.5% significance level when the true difference between the means is 0, the standard deviation of the paired differences is 0.510, and the equivalence limits are -0.17 and 0.17. Considering a 10% drop-out rate, total sample size required is 108.
Eligibility criteria	
Inclusion Criteria:
 
• Subjects \geq 30 years of age• Visible bilateral NLFs that were approximately symmetrical both and of equal severity with a rating of moderate or severe (assessed at the deepest part)• Able to follow study instructions and likely to complete all required visits• Signed informed consent 
Exclusion criteria:
 
• History of bleeding disorders or patients receiving or recently exposed (\leq 3 weeks) to continuous treatment with thrombolytics, anticoagulants,

	
platelet inhibitors, or NSAIDs
 
• Acute herpetic eruption• Known susceptibility to keloid formation, hypertrophic scarring or clinically significant skin pigmentation disorders• Known sensitivity to local anesthetics of the amide type (such as lidocaine), history of hypersensitivity to gram-positive bacterial proteins, history of multiple severe allergies, history of anaphylactic shock• Known hypersensitivity to any component of the study drugs or excipients (like hyaluronic acid)• History of receiving immune therapy or a history of autoimmune disease• History of active chronic debilitating systemic disease• History of connective tissue disease, history of malignancy (excl. non-melanoma skin cancer) within past 5 years• Clinically significant active dermatologic disorders within 6 months• Use in the 4 weeks before study randomization (or intent to use during the study) of oral retinoids, OTC or prescription antiwrinkle treatments, microdermabrasion, or chemical peels in the NLF area• Any prior cosmetic procedure or tissue augmentation at the NLF injection site in 1 year before study entry (or intent to undergo such a procedure during the study)• Pregnancy or breastfeeding
Randomization	The subjects will be randomized into two possible treatment groups. The first treatment group will receive Lunaphil Ultra on the right side and Juvéderm® Ultra 4 on the left side of their face. The second treatment group will receive Juvéderm® Ultra 4 on the right side and Lunaphil Ultra on the left side of their face. The randomization plan of the subjects will be carried out centrally using an R-CRAN software version 4.0.3. Blocks (with the size of 2) will be made using permuted block randomization for a total of 108 subjects (1:1 allocation ratio).
Blinding	To prevent the influence of any bias caused by knowing the intervention face-side, the study will be double-blinded. Hence, patients and those who assess the study outcomes will remain unaware of allocation to test- or reference-Hyaluronic acid.
Intervention	Subjects will be treated with Juvéderm® Ultra 4 in one NLF and Lunaphil Ultra in the opposite NLF.

	
Two treatments will be allowed over a 2-week period (initial treatment plus one touch-up) to achieve optimal correction of the NLFs. The level of correction will be assessed by the evaluating investigator at week 2 after the initial treatment and, if less than optimal, the treating investigator will be directed to retreat the undercorrected NLF(s).

Outcomes	
Efficacy and safety outcomes
 
Primary outcome:
 
Mean level of improvement from baseline in NLF severity score by WSRS (wrinkle severity rating scale) at 24 weeks
 
Secondary outcomes:
 
• Number of subjects with improvement score for the 5-point Physician Global Aesthetic Improvement Scale (PGAIS) at 24 weeks• Proportion of NLFs maintaining a clinically significant improvement in NLF severity score (≥ 1-point reduction from baseline) at 24 weeks• Volume to Obtain Optimal Cosmetic Result (Initial Treatment + Touch-up)• Number of NLFs receiving touch-up treatment• Incidence of adverse events (Injection Site Reactions) and incidence of adverse events (Injection Site Reactions) based on severity
Statistical Plan	
Processes of cleaning, inspecting, and transforming will be done in the procedure of data analysis. Also, the descriptive analysis will be performed using frequency and percentage, average and standard deviation regarding the type of the variables.
 
Primary Endpoint:
 
The mean level of improvement from baseline in NLFs severity score based on assessments by evaluating investigators will be analyzed using a paired t-test or a signed-rank test.
 
Secondary Endpoint:
 
The number of patients with improvement score for the PGAIS will be

	
analyzed using a McNemar test.
 
The proportion of NLFs with clinically significant improvement will be analyzed using a McNemar test.
 
Injection volume to obtain optimal result will be analyzed with a paired t-test or a signed-rank test.
 
The number of NLFs receiving touch-up treatment will be analyzed using a McNemar test.
 
Safety:
 
The safety data will be analyzed primarily using summary statistics. The incidence, frequency, and severity of adverse events (Injection Site Reactions) will be reported.

Withdrawal Criteria	
• Withdrawal of consent by the patient• Noncompliance, including refusal of study medical requirements, refusal of procedures as stated in the study protocol, or use of prohibited medications• The occurrence of an undesirable event that causes the investigator to consider the patient's exclusion from the study• Not possible to follow the patient's condition (Loss to follow-up)• Change in patient's conditions which needs change of treatment due to investigator decision or administration of prohibited medications in protocol

Study Timeline

Time point	Study period					
	Screening	Intervention			Visit 3	Visit 4
Time	Screening visit	Visit 1	Visit 2, * (Touch-up)	Visit 2, ** 3days	12 weeks ± 3days	24 weeks ± 3days
Informed consent	×					
Eligibility Criteria	×					
Randomization and allocation		×				
Medical History	×					
Face photography	×	×	×	×	×	×
Intervention		×	×			
NLF severity score assessment	×		×	×	×	×
PGAIS assessment		***	×	×	×	×
Concomitant Medications	×	×	×	×	×	×
Adverse Events reporting	×	×	×	×	×	×

* Two treatments will be allowed over a 2-week period (initial treatment plus one touch-up) to achieve optimal correction of the NLFs. The level of correction will be assessed by the evaluating investigator at week 2 after the initial treatment and, if less than optimal, the treating investigator will be directed to retreat the under corrected NLF(s).

** This visit is only conducted in patients with touch-up injection.

*** PGAIS in visit 1 is assessed after the intervention.

List of Abbreviations and Definition of Terms

Abbreviation	Description
ADL	Activities of Daily Living
ADR	Adverse Drug Reaction
AE	Adverse Event
CRF	Case Report Form
CTCAE	Common Terminology Criteria for Adverse Events
GCP	Good Clinical Practice
HA	Hyaluronic Acid
ICH	International Council for Harmonization of Technical Requirements for
MedDRA	Medical Dictionary for Regulatory Activities
NLF	Nasolabial Fold
NSAID	Non-Steroidal Anti-Inflammatory Drug
OTC	Over-the-Counter
PGAIS	Physician Global Aesthetic Improvement Scale
PMS	Postmarketing Surveillance
PT	Preferred Term
SOC	System Organ Class
SOP	Standard Operating Procedure
WHO	World Health Organization
WSRS	Wrinkle Severity Rating Scale

Section 1: Administrative information

Title and Trial registration

A phase IV, randomized, double-masked, active controlled, within-subject equivalency clinical trial to compare effectiveness and safety of Lunaphil Ultra (Hyaluronic acid, produced by Espad Pharmed Co.) versus Juvéderm® Ultra 4 (Hyaluronic acid, produced by Allergan Co.) for the management of moderate or severe nasolabial folds (NLFs)

Ethics Approval Number

IR.TUMS.MEDICINE.REC.1400.1011

SAP Version (SAP version number with dates)

Version: 1.0, Date: 2021 August 14

Section 2: Introduction

Introduction

This Statistical Analysis Plan (SAP) provides a detailed and comprehensive description of the planned statistical analyses for the Phase IV randomized, double-blind, parallel-group, active-controlled clinical trial designed to assess the therapeutic equivalence in efficacy and safety of Lunaphil Ultra (Hyaluronic acid, produced by Espad Pharmed Co.) versus Juvéderm® Ultra 4 (Hyaluronic acid, produced by Allergan Co.) in managing moderate or severe NLFs.

The objective of this SAP is to outline the statistical methodologies and analysis principles that will be applied to evaluate the primary and secondary endpoints of the study, as well as the handling of missing data, analysis sets, and subgroup analyses. This SAP is intended to ensure transparency and reproducibility of the planned analyses, and it has been finalized prior to database lock and unblinding of the study data.

Rationale and Background

Skin aging is a complex and multifactorial process resulting in various functional and aesthetic changes in the skin (1). It is an inevitable process that can be described clinically as features of wrinkles, sun

spots, uneven skin color, and sagging skin (2). Additional clinical findings include tear trough, a drop of the angle of the mouth, loss of definition in the mandibular border, platysmal bands, evident veins, and NLFs as one of the typical clinical manifestations of facial aging (3).

The perception of health and age is a critical aspect in the common judgment of attractiveness and people are judged to be less attractive as they age (4). Attractiveness influences both self-perception and social behavior and is related to traits such as self-confidence and social acceptance. Therefore, aesthetic interventions can improve psychological well-being and quality of life (5).

Dermal fillers are widely used for the correction of deep wrinkles, including NLFs. Treatments with dermal fillers provide favorable aesthetic outcomes with minimal invasiveness and no downtime following surgical procedures (6). Hyaluronic acid (HA) fillers, the most popular dermal fillers (7), demonstrate desirable effects on the fibroblast phenotype, including higher cell proliferation and type I collagen synthesis (8). HA fillers have predictable efficacy, a good safety profile, quick recovery, and simplicity in administration (9, 10).

Different factors, including HA concentration, polymer chain length, and crosslinking degree or technology, influence filler properties such as the requisite needle size, particle size, duration, extrusion force, and elastic Modulus (G'). All of these factors will critically influence product selection and indication (11). Among these factors, crosslinking is essential to slowing down the enzymatic degradation rate of the HA by endogenous hyaluronidase and prolonging the product's half-life. The extent of crosslinking strongly impacts the biophysical and biological properties of a filler, including tissue integration, water uptake, resistance to degradation, and filler biocompatibility and consequently might have clinical implications (12).

Lunaphil Ultra intradermal filler is a cross-linked HA soft tissue filler manufactured by Espad Pharmed Company. It contains 24 mg/ml of HA and 0.3% lidocaine as a supplemental anesthetic. Since pain is the most commonly reported complaint with dermal fillers, a local anesthetic like lidocaine is included in their formulation to reduce procedural pain and bypass the need for additional anesthesia (13).

The aim of this study is to compare the effectiveness and safety of Lunaphil Ultra (Hyaluronic acid, produced by Espad Pharmed Co.) versus Juvéderm® Ultra 4 (Hyaluronic acid, produced by Allergan Co.) in managing moderate or severe NLFs.

Objectives

This study aims to assess the safety and effectiveness of Lunaphil Ultra for the management of moderate or severe nasolabial folds (NLFs).

Primary objective(s)

Mean level of improvement from baseline in NLF severity score by WSRS at week 24

Secondary objective(s)

1. Number of subjects with an improvement score based on PGAIS at week 24
2. Proportion of NLFs maintaining a clinically significant improvement in NLF severity score (≥ 1 - point reduction from baseline) at week 24
3. The injected volume to obtain optimal aesthetic result (initial treatment + touch-up)
4. The number of NLFs receiving touch-up treatment
5. The incidence, severity and causal relationship of adverse events

Section 3: Research Methods

Study Design

This is a randomized, double-masked, active controlled, within-subject, and equivalency study to compare the effectiveness and safety of Lunaphil Ultra (Hyaluronic acid, produced by Espad Pharmed Co.) versus Juvéderm® Ultra 4 (Hyaluronic acid, produced by Allergan Co.) for the management of moderate or severe NLFs.

Intervention

Subjects will be treated with Juvéderm® Ultra 4 in one NLF and Lunaphil Ultra in the opposite NLF. Two treatments will be allowed over a 2-week period (initial treatment plus one touch-up) to achieve optimal correction of the NLFs. The level of correction will be assessed by the evaluating investigator at week 2 after the initial treatment and, if less than optimal, the treating investigator will be directed to retreat the undercorrected NLF(s).

Randomization

The subjects will be randomized into two possible treatment groups. The first treatment group will receive Lunaphil Ultra on the right side and Juvéderm® Ultra 4 on the left side of their face. The second treatment group will receive Juvéderm® Ultra 4 on the right side and Lunaphil Ultra on the left side of their face. The randomization plan of the subjects will be carried out centrally using an R-CRAN software version 4.0.3. Blocks (with the size of 2) will be made using permuted block randomization for a total of 108 subjects (1:1 allocation ratio).

Blinding

To prevent any bias arising from awareness of face-side allocation, this study will be performed in a double-blind manner. For each participant, one side of the face will receive the investigational hyaluronic acid product and the other side will receive the reference Hyaluronic acid product, according to the pre-specified randomization plan. Both the participants and all investigators responsible for administering injections and assessing outcomes will remain blinded to the allocation throughout the study.

Sample size

In an equivalence test of means using two one-sided tests on data from a paired design, a sample size of 97 achieved 80% power at a 2.5% significance level. When the true difference between the means was 0.000, the standard deviation of the paired differences was 0.510, and the equivalence limits were -0.170 and 0.170. Considering a drop-out rate of 10%, total sample size required is 108.

Study Population Criteria

Inclusion Criteria

1. Subjects \geq 30 years of age

2. Visible bilateral NLFs that are approximately symmetrical and have an equal severity ranging from moderate to severe (assessed at the deepest part)
3. Able to follow study instructions and likely to complete all required visits
4. Signed informed consent

Exclusion Criteria

1. History of bleeding disorders or participants receiving or recently exposed (≤ 3 weeks) to continuous treatment with thrombolytics, anticoagulants, platelet inhibitors, or NSAIDs
2. Acute herpetic eruption
3. Known susceptibility to keloid formation, hypertrophic scarring or clinically significant skin pigmentation disorders
4. Known sensitivity to local anesthetics of the amide type (such as lidocaine), history of hypersensitivity to gram-positive bacterial proteins, history of multiple severe allergies, history of anaphylactic shock
5. Known hypersensitivity to any component of the study products or excipients (like hyaluronic acid)
6. History of receiving immune therapy or a history of autoimmune disease
7. History of active chronic debilitating systemic disease
8. History of connective tissue disease, history of malignancy (except for non-melanoma skin cancer) within the last 5 years
9. Clinically significant active dermatologic disorders within the last 6 months
10. Use of oral retinoids, OTC or prescription antiwrinkle treatments, microdermabrasion, or chemical peels in the NLF area within the last 4 weeks or intention to use them during the study
11. Any prior cosmetic procedure or tissue augmentation at the NLF injection site within 1 year before study entry (or intent to undergo such a procedure during the study)
12. Pregnancy or breastfeeding

Withdrawal Criteria

1. Withdrawal of consent by the participant
2. Noncompliance, including refusal of study medical requirements, refusal of procedures as stated in the study protocol, or use of prohibited medications
3. The occurrence of an undesirable event that causes the investigator to consider the participant's exclusion from the study
4. Not possible to follow the participant's condition (Loss to follow-up)

5. Change in participant's conditions, which needs change of treatment due to investigator decision or administration of prohibited medications in the protocol

Data sources and measurement

All data will be collected by specialists and recorded in a booklet comprising five visits. Baseline information (demographics, past medical history, history of filler injection, patients' medications), intervention information (e.g., dosage at visit 1 and touch up), WSRS, and PGAIS will be recorded.

All adverse events (AEs) will be documented and categorized according to their frequency, severity (graded using the Common Terminology Criteria for Adverse Events version 5.0) (14), and their assessed causality, following the World Health Organization guidelines (15). The AEs will be reported using the Medical Dictionary for Regulatory Activities (MedDRA) under both the preferred term (PT) and system organ class (SOC) (16). Serious adverse events (SAEs) will be documented in compliance with the E2B(R2) guideline (17) and will be defined as any AE that “results in death, is life-threatening, requires inpatient hospitalization or prolongation of existing hospitalization, results in persistent or significant disability/incapacity, is a congenital anomaly/birth defect, or other medically important condition.”

Section 4: General issues for statistical analysis

Analysis populations

Primary efficacy will be analyzed on a per-protocol population. Also, the primary outcome and secondary key variables of the study will be examined on the intention-to-treat population, and sensitivity analysis will be used to compare the primary outcome in the two populations. All analyzes of complications will be performed based on the safety population.

1. Per-protocol population: all patients who were randomly treated with the study drug and did not have a major deviation from the protocol.
2. Intention-to-treat population: all patients randomly assigned to one of the treatment groups. Patients are analyzed according to the treatment they received randomly.
3. Safety population: All patients who randomly received at least one dose of the study drug. Patients are analyzed according to the treatment they actually received.

Protocol violations and deviations

